## octapharma® Case Safety Report Form

Local Log Number \_\_\_\_\_

Concomitant Medication 6					
Trade name			Active ingredient		
Dosage (#)	Dosage (unit)	Frequency (#)	Interval (#)	Interval (unit)	Route
Indication					
Concomitant Medication 7					
Trade name			Active ingredient		
Dosage (#)	Dosage (unit)	Frequency (#)	Interval (#)	Interval (unit)	Route
Indication					
Concomitant Medication 8					
Trade name			Active ingredient		
Dosage (#)	Dosage (unit)	Frequency (#)	Interval (#)	Interval (unit)	Route
Indication					
Concomitant Medication 9					
Trade name			Active ingredient		
Dosage (#)	Dosage (unit)	Frequency (#)	Interval (#)	Interval (unit)	Route
Indication					
Concomitant Medication 10					
Trade name			Active ingredient		
Dosage (#)	Dosage (unit)	Frequency (#)	Interval (#)	Interval (unit)	Route
Indication					

## Case Safety Report Form

Local Log Number \_\_\_\_\_

4. SUSPECT PRODUCT(S) (Information on treatment that led to the adverse reaction(s))					
4.1 Overall treatment regimen of suspect product(s)					
Suspect Product 1					
Product/Generic (incl. strength)		Batch number(s)			Start date (dd/mm/yyyy)
Dosage (#)	Dosage (unit)	Frequency (#)	Interval (#)	Interval (unit)	Route
Infusion rate	Duration (#)	Duration (unit)	Indication		
Suspect Product 2					
Product/Generic (incl. strength)		Batch number(s)			Start date (dd/mm/yyyy)
Dosage (#)	Dosage (unit)	Frequency (#)	Interval (#)	Interval (unit)	Route
Infusion rate	Duration (#)	Duration (unit)	Indication		
Suspect Product 3					
Product/Generic (incl. strength)		Batch number(s)			Start date (dd/mm/yyyy)
Dosage (#):	Dosage (unit):	Frequency (#)	Interval (#)	Interval (unit):	Route
Infusion rate	Duration (#)	Duration (unit)	Indication		
4.2 Previous Treatment with suspect product(s)					
Did the patient receive previous treatment with suspect product(s) and/or similar product(s)?					
Name of product _____			Treatment date (approx. period): _____		
Did the patient experience adverse reaction in previous treatment?					
Adverse reaction _____			Reaction date (dd/mm/yyyy) _____		Outcome _____

octapharma®

## Case Safety Report Form

Local Log Number \_\_\_\_\_

Name of product _____	Treatment date (approx. period) _____		
Did the patient experience adverse reaction in previous treatment?  Yes  No  Unknown			
Adverse reaction _____ Reaction date (ddmmyyyy) _____ Outcome _____			
Name of product _____ Treatment date (approx. period) _____			
Did the patient experience adverse reaction in previous treatment?  Yes  No  Unknown			
Adverse reaction _____ Reaction date (ddmmyyyy) _____ Outcome _____			
5. ADVERSE REACTION(S) (Adverse reaction(s) according to the primary reporter's words and/or phrases)			
* Latency: Time since the treatment with suspect drug(s)			
Adverse Reaction 1			
Adverse reaction/ diagnosis:			Start date (ddmmyyyy) _____ End date (ddmmyyyy) _____
Duration:	Duration (unit):	Latency* (incl. units):	Outcome:
Adverse Reaction 2			
Adverse reaction/ diagnosis:			Start date (ddmmyyyy) _____ End date (ddmmyyyy) _____
Duration:	Duration (unit):	Latency* (incl. units):	Outcome:
Adverse Reaction 3			
Adverse reaction/ diagnosis:			Start date (ddmmyyyy) _____ End date (ddmmyyyy) _____
Duration:	Duration (unit):	Latency* (incl. units):	Outcome:

octapharma®

Case Safety Report Form

Local Log Number  
\_\_\_\_\_

1. Action taken with respect to suspect product(s)? (state product for resp action in case different actions were taken for different products)	Product	Action
2. If product was withdrawn, did reaction(s) stop/improve after stopping suspect product without patient receiving remedial therapy?	 Yes  No  Unknown  NA	
3. Did reaction(s) reappear after reintroduction?	 Yes  No  Unknown  NA	
Remedial Therapy (Information on therapy to treat the adverse reaction(s).)	If yes, please specify:	

octapharma®

Case Safety Report Form

Local Log Number \_\_\_\_\_

6. LABORATORY TEST		
Laboratory tests performed (Any tests relating to the adverse reaction(s) including results, units, and normal range.)		 Yes  No  Unknown
Lab Test 1		
Test name / Which test was performed?		
Test date (dd/mm/yyyy)	Test result	Test result unit
Comment		
Lab Test 2		
Test name / Which test was performed?		
Test date (dd/mm/yyyy)	Test result	Test result unit
Comment		
Lab Test 3		
Test name / Which test was performed?		
Test date (dd/mm/yyyy)	Test result	Test result unit
Comment		

octapharma®

## Case Safety Report Form

Local Log Number  
\_\_\_\_\_

Lab Test 4		
Test name / Which test was performed?		
Test date (dd/mm/yyyy)	Test result	Test result unit
Comment		
7. CASE REPORT ASSESSMENT (Provided by the primary reporter)		
7.1 Seriousness Assessment		
 Non-Serious  Not provided by the primary source		
 Serious		
IF SERIOUS , please choose at least one of the following criteria (defined by the primary reporter):		
 Patient hospitalized	From*: _____	To*: _____
 Hospitalization prolonged	From*: _____	To*: _____
 Life threatening	*Date format (dd/mm/yyyy)	
 Resulting in persistent or significant disability/incapacity		
 Resulting in congenital anomaly or birth defect		
 Medically significant	_____	
 Fatal (please complete section below)		
 Other, please specify:	_____	
IF FATAL , please complete:		
Date of death: (dd/mm/yyyy)	Autopsy performed:  Yes  No  Unknown	
Cause of death: _____		

## Case Safety Report Form

Local Log Number

### 7.2 Causality Assessment

Relatedness of the observed symptoms/reactions to the administration of suspected Octapharma product:

Probably related  Possibly related  Unlikely related  Not related

Unclassifiable/Unknown Comment:

Other possible cause(s) of the adverse reaction(s):

Underlying disease  Concomitant medication  Other suspected product (non-Octapharma)  
 Other, please specify:

### 8. NARRATIVE / DETAILED DESCRIPTION OF EVENT

(A detailed description of the chronology and outcome of the adverse reaction(s))

### 9. OTHER COMMENTS

Was Competent Authority (ies) informed?	If yes, please enter Authority reference#:
Comment	

## Annex 3    Pregnancy Form

octapharma Pharmazeutika Produktionsges.m.b.H.		CDSU Ref:
Pregnancy Form		Page A-1
Reporter Details		
Surname		Firstname
Qualification	 general practitioner physician  obstetrician / gynaecologist  consumer  other	
Address		
Tel		Fax
Email		
Please complete the form as appropriate and accurately as possible, date, sign and return as soon as possible to the Octapharma Local Safety Office ( refer to the protocol Section 13, Annex 2) WE THANK YOU FOR YOUR CO-OPERATION		

[figure not shown]
Section A Maternal Information				
Patient (initials)	Date of birth (dd/mm/yyyy)	Age	Height (cm)	Weight (kg)
A.1 Obstetrical history				
No of previous pregnancies		No of live-births		
Result of previous pregnancies (tick as appropriate and please specify gestational age)				
 Miscarriage				
 Elective termination				
 Late foetal death				
 Ectopic pregnancy				
 Molar pregnancy				
 Other				
Did any OTHER complication occur during previous pregnancies?	 No	 Yes ->		
Or were there any foetal/ neonatal abnormalities?	 No	 Yes ->		
History of subfertility and treatment	 No	 Yes ->		
A.2 Maternal Medical History				
 Hypertension	 Allergic disease	 Hepatitis		
 Diabetes	 Heart disease	 AIDS		
 Seizure disorder	 Depression	 Other		
 Thyroid disorder	 Psychiatric disorder			
 Asthma	 Sexually transmitted disorder			
A.3 Current Pregnancy				
Date of last menstrual period (LMP) (dd/mm/yyyy)	Gestational age at the time of this report (weeks)	Estimated date of delivery (dd / mm / yyyy )		

101SOP220/02 Appendix 2 ( Version 00 )

octapharma Pharmazeutika Produktionsges.m.b.H.	Pregnancy Form
CDSU Ref:	Page A-2

A.3 Current Pregnancy					
Date of last menstrual period (LMP) (dd/mm/yyyy)		Gestational age at the time of this report (weeks)		Estimated date of delivery (dd / mm / yyyy )	
No of foetuses?		Treatment for infertility?		 No	 Yes
Medications taken during pregnancy (incl. OTC products and pregnancy supplements)					
Drug & Batch	Dose/Unit	Route	From	To	Indication
Recreational Drug Use					
Tobacco	 No	 Yes	Amount:		
Alcohol	 No	 Yes	Amount:		
Ilicit Drugs	 No	 Yes	Amount:		
Previous Immunity to					
 Rubella	 Toxoplasmosis	 Cytomegalovirus	 Listeria		
Antenatal Check-Up					
	Date	Significant observations			
 Ultrasound					
 Amniocentesis					
 Maternal Serum Alpha-Fetoprotein (AFP)					

octapharma Pharmazeutika Produktionsges.m.b.H.		Pregnancy Form
CDSU Ref:		
 Chorionic Villi Biopsy		
 Umbilical Blood Sampling		
 Biophysical Electrical Monitoring		
 Other		
A.4 Familial History		
Spontaneous abortion	 Mother (Maternal)  Father (Maternal)	 Mother (Paternal)  Father (Paternal)
 Hereditary disease ->		
 Anomalies / Malformation ->		
 Psychomotor retardation ->		
A.5 Additional Comments		
Reporter Name:	Date of report:	Signature:

 Pharmazeutika Produktionsges.m.b.H.		Pregnancy Form		
CDSU Ref:		Page B-1		
Section B Paternal Information (If appropriate)				
Patient (initials)	Date of birth (dd/mm/yyyy)	Age	Height (cm)	Weight (kg)
B.1 Medical History				
			From	To
B.2 Medications around time of conception				
Drug & Batch	Dose/Unit	Route	From	To
B.3 Additional Comments				
				
Reporter Name:	Date of report:	Signature:		

octapharma Pharmazeutika Produktionsges.m.b.H.		CDSU Ref:
Pregnancy Form		Page C-1
Reporter Details		
Surname		Firstname
Qualification	 general practitioner physician  obstetrician / gynaecologist  consumer  other	
Address		
Tel		Fax
Email		
Please complete the form as appropriate and accurately as possible, date, sign and return as soon as possible to the Octapharma Local Safety Office ( refer to the protocol Section 13, Annex 2) WE THANK YOU FOR YOUR CO-OPERATION		

**Section C Neonatal Information**

Neonatal (initials)	Date of birth (dd/mm/yyyy)	Gestational age (LMP) at birth	Gender
			 Male  Female
Height (cm)	Weight (kg)	Head circumference (cm)	Apgar score (1 min)
			Apgar score (5 min)
 Live birth  Foetal death (please complete C2)  Elective termination (please complete C2)			
C.1 Delivery details			
Mode of delivery	 Natural  Caesarean section		
Labour / delivery complications (e.g. foetal distress, amniotic fluid abnormal)	 No  Yes ->		
Abnormal placenta	 No  Yes ->		
Malformations/ anomalies / diseases diagnosed at birth	 No  Yes ->		
Dysmaturity	 No  Yes ->		
Need for resuscitation/ admission in C.U.	 No  Yes ->		
Other treatments	 No  Yes ->		
C.2 Foetal Information			
Foetal examination performed	Results if available (eg gender, anomalies, identified cause of death):  No  Yes ->		

octapharma Pharmazeutika Produktionsges.m.b.H. CDSU Ref:	Pregnancy Form Page C-2	
C.3 Additional Comments		
Reporter Name:	Date of report:	Signature:

Property of Octapharma. Do not copy or distribute without written permission

 octapharma Pharmazeutika Produktionsges.m.b.H.		CDSU Ref:
Pregnancy Form		Page D-1
Reporter Details		
Surname		Firstname
Qualification	 general practitioner physician  obstetrician / gynaecologist  consumer  other	
Address		
Tel		Fax
Email		
Please complete the form as appropriate and accurately as possible, date, sign and return as soon as possible to the Octapharma Local Safety Office ( refer to the protocol Section 13, Annex 2)		
WE THANK YOU FOR YOUR CO-OPERATION		

octapharma Pharmazeutika Produktionsges.m.b.H.		Pregnancy Form			
CDSU Ref:		Page D-2			
D.2 Drug Therapies					
Drug & Batch	Dose/Unit	Route	From	To	Indication
D.3 Additional Comments					
Reporter Name:	Date of report:	Signature:

1 STUDY INFORMATION

1.1 Primary objective

The primary objective of this study is to characterize the bleeding and treatment pattern of patients with type 3, type 2 (except 2N), or severe type 1 VWD undergoing routine on-demand treatment with a VWF-Containing Product (VCP).

1.2 Secondary objective

The secondary objectives of this study are to:

- Assess the quality of life (QoL) of VWD patients undergoing on-demand treatment with a VCP
- Assess the safety of the VCP used for on-demand VWD treatment

The following objectives are also pursued except for Croatian centers:

- Determine the effectiveness of the VCP used in the treatment of bleeding episodes (BEs)
- Determine the effectiveness of the VCP used in surgical prophylaxis
- Assess the patients' joint status using the Hemophilia Joint Health Score (HJHS)
- Assess the menstrual bleeding intensity of female patients of child-bearing potential

1.3 Study design

This is a prospective, multicenter, international, non-controlled non-interventional study (NIS).

1.4 Planned sample size

No formal sample size calculations were performed. The sample size of 55 patients was chosen based on feasibility and to allow data summaries to be produced. However, with a sample size of 55, a two-sided 95% confidence interval for the mean ABR will extend ± 0.8 from the observed mean, assuming that the standard deviation is 3 or less and the confidence interval is based on the large sample z statistic.

2 GENERAL INFORMATION

2.1 Background details

All study data will be transferred to a SAS database (version 9.4 or later) for statistical analysis purposes. Data will be imported from the Data Capture System OPVerdi via validated SAS programs. If applicable external data will also be transferred to SAS for presentation of these data in the statistical analyses.

2.2 Deviations from the trial protocol with regard to statistical analyses

For calculation of annualized bleeding rates (ABR) surgery periods will be subtracted from the time period under observation, and bleeding episodes occurred during surgery periods will not be counted as defined in protocol. However, the definition of surgery periods has been clarified. Protocol definition "3 hours before the start of surgery to the time the patient returns to

Statistical Analysis Plan	Version 3.0		Page 7 of 17
Sponsor	Octapharma	Protocol No	WIL-29

on-demand treatment" was updated to "day of surgery until last VCP treatment for surgery". Bleeding episodes that occurred on the day of surgery but before start of surgery will be counted towards the ABR.

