### 8.3.3 Exclusion Criteria

Patients who meet any of the following criteria are *not* eligible for the study:

1. Patients currently on prophylaxis for VWD (except for perioperative prophylaxis) as well as patients having received treatment once a month for menstrual bleeding, but not for any other bleeds
2. Patients whose VWD treatment is planned to be switched from on-demand to prophylactic treatment in the next 6 months
3. History, or current suspicion, of VWF or FVIII inhibitors
4. Medical history of a thromboembolic event within 6 months before enrolment
5. Severe liver or kidney diseases as described in the medical records
6. Female patients with an existing or suspected pregnancy or who are breast-feeding at the time of enrolment
7. Change in hormonal contraception within 6 months before enrolment
8. Cervical or uterine conditions causing abnormal uterine bleeding (including infection or dysplasia)
9. Other coagulation disorders or bleeding disorders due to anatomical reasons
10. Participation in an interventional clinical study during the 6-month of study period
11. Inability to complete the patient diary to reliably evaluate the type, frequency, and treatment of BEs during the 6-month study period

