### 8.4.2 Study Duration

The overall study duration will be approximately 2 years. Each patient will be followed for around 6 months from the time of enrolment. The study will be considered completed at the time of database lock.

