6 DERIVATIONS AND TRANSFORMATIONS

6.1 Formulas for derived variables

Variable	Description
Durations between two dates	Later date minus earlier date plus 1, expressed in days. (Remark: Duration will be 1, if both dates are the same.)
Surgery Period	(Date of surgery – date of last VCP treatment for surgery + 1)/365.25
Total Annualized Bleeding Rate (TABR)	Number of bleedings excluding menstrual bleedings / (date of study completion – date of screening + 1)/365.25 (Surgery periods, and BEs occurring within these surgery periods, will be excluded from the calculation of TABR. BEs occurring at day of surgery but prior to start of surgery/start of treatment for surgery will be included into calculation)
Spontaneous Annualized Bleeding Rate (SABR)	Number of spontaneous bleedings / (date of study completion – date of screening + 1)/365.25 (Surgery periods, and BEs occurring within these surgery periods, will be excluded from the calculation of SABR. BEs occurring at day of surgery but prior to start of surgery/start of treatment for surgery will be included into calculation)
Traumatic Annualized Bleeding Rate (TRABR)	Number of spontaneous bleedings / (date of study completion – date of screening + 1)/365.25 (Surgery periods, and BEs occurring within these surgery periods, will be excluded from the calculation of TRABR. BEs occurring at day of surgery but prior to start of surgery/start of treatment for surgery will be included into calculation)
Heavy Menstrual Bleeding Rate (HMBR)	Number of heavy menstrual bleedings* / (date of study completion – date of screening + 1)/365.25 (* for a definition refer to section 6.4)
ED	Exposure day = each calendar day the subject received VCP

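### The SAP takes the whole day of surgery out of the bleeding-rate denominator but counts bleeds from earlier that day, and gives two different cut-offs for those bleeds

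*SAP*

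**What the plan says.** Protocol 8.2.1 and SAP 4.7.1 exclude both surgery periods and the bleeds within them from TABR, without exception. Protocol 8.5.6.2 starts the preoperative period no more than 3 hours before the operation.

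SAP 2.2 replaces this with a period that runs from the day of the operation to the last VCP given for it. It confirms that "surgery periods will be subtracted from the time period under observation", and then adds: "Bleeding episodes that occurred on the day of surgery but before start of surgery will be counted towards the ABR".

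SAP 6.1 builds the surgery period from calendar dates, counting both end dates, so the day of surgery is removed in full. The TABR, SABR and TRABR rows each repeat the exception in other words: "BEs occurring at day of surgery but prior to start of surgery/start of treatment for surgery will be included into calculation". No row limits the period to the interval between screening and study completion.

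**The concern.** A rate needs its events and its time at risk to come from the same interval. Here the hours before the operation supply bleeds but no time, which pushes the rate up for patients who have surgery.

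The two cut-offs also disagree. Section 2.2 uses the start of the operation. Section 6.1 joins that with the start of surgical treatment by a slash and does not say which governs. Protocol Table 6 places the preoperative dose within 3 hours before surgery, and the surgery set in SAP 3.3 requires VCP before the operation. Each such surgery therefore has an interval in which two programmers could classify the same bleed differently.

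TABR is the only primary endpoint and is meant as a historical comparator for a prophylaxis study (Protocol 6.2). Its derivation should leave no such choice open once the data are visible.

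**Working it through.** **The plan's own figure.** SAP 1.4 states that "a two-sided 95% confidence interval for the mean ABR will extend ± 0.8 from the observed mean". The inputs given there are an SD of at most 3 and a z-based interval. With N = 55: 1.96 × 3 / √55 = 0.793, which rounds to 0.8. This is reproduced and is the yardstick below.

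**Inputs.** Protocol 8.4.2: "Each patient will be followed for around 6 months from the time of enrolment". I take 183 days; a range of 168 to 213 days is my assumption. Bleed counts and lengths of surgery periods are also assumptions, because the documents give none. The 6.1 formulas are read by their evident intent: TABR = bleeds × 365.25 / (window days − surgery-period days).

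**1. The lost day.** Take a 183-day window, a one-day surgery period, 3 other bleeds and 1 bleed on the morning of surgery.
- As written: 4 × 365.25 / 182 = 8.03 per year.
- Keeping the day in the time: 4 × 365.25 / 183 = 7.98.
- Dropping the morning bleed instead: 3 × 365.25 / 182 = 6.02.

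Against keeping the day, the excess is 183/182 − 1 = 0.55%. On the mean of 55 it is (8.03 − 7.98)/55, which is under 0.001. A 10-day surgery period gives 174/173 − 1 = 0.58%, practically the same. These are upper bounds, since only the hours before the operation are mismatched. With an assumed 10:00 start (0.42 day), the excess is 182.42/182 − 1 = 0.23%.

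**2. The two cut-offs.** One bleed that is in under one wording and out under the other changes:
- that patient's TABR by 365.25/182 = 2.0 per year (1.7 to 2.2 for windows of 213 to 168 days);
- the mean of 55 by 2.007/55 = 0.036, or 0.18 if five patients are affected;
- the mean of a 6-patient subgroup by 2.007/6 = 0.33. Protocol 8.3.1 asks for at least 6 patients with type 3 VWD, and SAP 3.4 reports TABR and SABR by type.

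How often: 3 hours is 0.125/365.25 = 0.00034 year. At an assumed 5 to 20 bleeds per year, the expected number in that gap is about 0.002 to 0.007 per surgery.

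**3. Overhang past study completion.** Assume 3 bleeds, a 183-day window and 3 surgery days inside it. Limited to the window: 3 × 365.25 / 180 = 6.09. If the period runs 7, 14 or 21 days past completion and all of it is subtracted, the divisor is 173, 166 or 159 days. TABR is then 6.33, 6.60 or 6.89, which is +4%, +8% or +13% for that patient.

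**The case against.** The best defence is that 2.2 and 6.1 state a deliberate exception, that a specific rule overrides the general one in 4.7.1, and that losing part of one day is ordinary rounding in a date-based formula. Much of this stands. Counting a bleed that precedes the operation is reasonable, and the rounding is negligible against a half-width of 0.8. What does not stand is that 4.7.1 is left uncorrected, the matching time is still removed, and the two statements of the exception disagree.

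A reader might infer that the numerator is undefined as a whole. It is not: only a bleed in the short gap between preoperative treatment and the operation is ambiguous.

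A reader might also infer from the perioperative exemption in exclusion criterion 1 that patients enrol in mid-course and that days before screening are then subtracted, inflating TABR. The documents do not support that firmly. Section 2.2 subtracts from time under observation, and 4.1.2 confines rate calculations to documented periods. Protocol 8.5.6 asks for surgeries during participation, so the earlier surgery date is not clearly collected, and the direction of any error depends on whether it is. Inclusion criterion 3 requires current on-demand treatment, while Protocol 8.5.6.2 ends the postoperative period only on return to it, so entry in mid-course is itself doubtful.

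The same phrases in 2.2 and 4.1.2 might lead a programmer to cap the overhang in step 3. They hint at a limit but do not state one, so that part is an omission and not a wrong rule.

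**Conclusion.** The rule is wrong as written, with little numerical consequence. Bleeds and time on the day of surgery are treated differently, 4.7.1 contradicts 2.2 and 6.1, and 2.2 and 6.1 give different cut-offs.

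The day mismatch is worth about 0.55% at most for a surgery patient followed for 183 days with a one-day surgery period, and under 0.001 on the overall mean in the example. The cut-off conflict matters only if a bleed falls in a gap of about 3 hours. It would then be visible for that patient and in a small subgroup, but at 0.036 it is minor for the mean of 55. The number of surgeries is not given, so no total effect can be stated. The missing limit at study completion is a secondary clarification and matters only if VCP for surgery is recorded after that visit.

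**What to change.** Choose one cut-off and state it identically in SAP 2.2, 4.7.1 and the TABR, SABR and TRABR rows of 6.1. Start the subtracted surgery period at the date and time of that cut-off. Bleeds before it then count and the time before it stays in the denominator; bleeds after it do not count and the time is removed. Bleeds and time must both follow the clock: stopping the bleed count at a clock time while subtracting whole days leaves a mismatch in one direction or the other.

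Onset times of bleeds and times of injections are already collected (Protocol 8.5.3 and 8.5.4). The start time of the operation is not a listed item in Protocol Table 6, but SAP 4.7.3 relies on it, so confirm that the eCRF holds it. If the start of surgical treatment is chosen, say what applies when no dose precedes the operation. Add a line on surgery-day bleeds with no recorded time.

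Also state that only the part of a surgery period lying between screening and study completion is subtracted.

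The cost is a few sentences in the SAP and a small code change. If the operation start time is held, no new data are needed. Rates change slightly, and only in patients with surgery.
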